
3.0

*** Describe the study objectives. Please include primary aim and hypothesis, if applicable any secondary aims and hypotheses.**

A pulmonary telerehabilitation program provides a home-based option for patients unable or unwilling to participate in a traditional, center-based program. Studies have demonstrated that home-based pulmonary telerehabilitation programs are feasible, positively impact exercise endurance and quality of life measures, and are widely-accepted by patients *when initiated during periods of lung disease stability*. However, little is known regarding the feasibility or impact on physical activity, muscle function, exercise performance, and quality of life measures of a home-based pulmonary telerehabilitation program initiated immediately following an AECOPD. Consequently, we propose a two-year pilot study to evaluate the feasibility and impact of a home-based pulmonary telerehabilitation program on physical activity levels, muscle strength,

exercise performance, and quality of life measures in veterans with COPD following hospitalization with an AECOPD. Our aims include:

SA 1: To determine the feasibility of an eight-week home-based pulmonary telerehabilitation program in veterans with moderate to severe COPD initiated in the immediate post-hospitalization period following an AECOPD. *Hypothesis: An eight-week home-based pulmonary telerehabilitation program will have a high acceptance and adherence rate among veterans with moderate to severe COPD following hospitalization for an AECOPD.* We will track adherence to a home-based pulmonary telerehabilitation program consisting of eight weeks, three sessions per week of 1:1 supervised lower extremity endurance exercise and upper and lower extremity strength training, as well as an optional once-monthly support group via teleconferencing, immediately following hospitalization for an AECOPD. Exercise sessions will be conducted by an exercise physiologist via video conferencing. The support group will be conducted by the exercise physiologist or another staff member via teleconferencing. A satisfaction survey will be administered at the completion of the intervention. We will also assess factors (i.e. psychiatric attributes, social support) associated with adherence to obtain preliminary insights to optimize recruitment for a larger, randomized controlled trial.

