For safety purposes, participants in both the intervention and usual care group will also be enrolled in the hospital's telehealth program, which consists of daily monitoring of pulse oximetry, heart rate, blood pressure, and weight and regular contact with a telehealth provider. They will receive a pulse oximeter, automated blood pressure cuff, and scale as part of this program. An exercise physiologist will meet with participants randomized to the intervention group prior to hospital discharge but after informed consent is obtained to conduct a minimum of one to two face-to-face inpatient bedside pulmonary rehabilitation sessions. These sessions will be used to guide development of an individualized exercise prescription, determine participant oxygen requirements with exercise, and to assess participant safety. **Within one to six weeks post-discharge, participants in the intervention arm will begin pulmonary tele rehabilitation** sessions via 1:1 video conferencing with the exercise physiologist/study coordinator. The exercise physiologist/study coordinator will be located at VAPHS during these video conferencing sessions. These sessions will consist of: (1) a brief pre-exercise interview to assess symptoms and vital signs (pulse oximetry, pulse, blood pressure); (2) a warm-up period consisting of upper and lower extremity stretching exercises; (3) cycle ergometry with resistance settings and goal duration determined by the individualized exercise program developed prior to hospital discharge; (4) upper and lower extremity strength training with resistance bands; (5) a post-exercise debriefing interview to assess symptoms and post-exercise vital signs. Subjects will be offered the opportunity to enroll in a traditional facility-based pulmonary rehabilitation program.

Usual Care Group: Participants randomized to the usual care arm will also be enrolled in our institution's telehealth program, will receive an automatic blood pressure monitor, portable pulse oximeter, and scale. **Patients randomized to Usual Care will also be given an pedometer at hospital discharge to be worn everyday following discharge to track the patient's physical activity. Patients will receive a pedometer diary from study staff to record their daily steps from the pedometer.** We

also contact participants by telephone weekly to document their pedometer count. They will be permitted to keep the pedometer at the completion of the study.

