Development of the Initial Exercise Prescription: The exercise prescription will be developed based on exercise performance and self-reported modified Borg dyspnea scores, a scale widely used in both the clinical and research setting to measure a patient's perceived shortness of breath and effort, during the six minute walk and bedside pulmonary rehabilitation sessions. During the bedside sessions, the exercise physiologist/study coordinator will select the resistance setting on the cycle ergometer that allows the participant to perform five minutes of lower extremity cycle ergometry while achieving Borg scale ratings between four and six in accordance with the American Thoracic Society (ATS)/European Respiratory Society (ERS) Guidelines. Alternatively, interval training, which has resulted in similar improvements in walk distance and quality of life scores, will be used for those participants unable to perform five minutes of cycle ergometry. During the resistance training exercises, the resistance band workload that causes fatigue after eight to twelve repetitions will be selected for each target muscle group. Exercise performance during these bedside sessions combined with heart rate and exercise performance during six minute walk will be used to develop an individualized exercise prescription for home pulmonary telerehabilitation. [name] will provide guidance as needed on developing the initial exercise prescription for each participant.

Modification of the Exercise Prescription: The exercise prescription will be adjusted during the eight-week intervention to achieve modified Borg dyspnea scores of four to six during cycle ergometry and to target one to three sets of eight to twelve repetitions of each resistance training exercise per established guidelines. The resistance band level will be increased when a participant is able to complete three sets of twelve repetitions using correct technique through the full range of motion. [name] will provide guidance as needed on modification of the individualized exercise prescriptions throughout the eight-week intervention for each participant based on their performance. Other factors, including heart rate and blood pressure during exercise, will be considered when modifying the exercise prescriptions.

Measurement of physical activity: Participant activity will be measured with an pedometer provided at hospital discharge. The pedometer will be worn every day to track the participant's physical activity.

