Health-related quality of life assessments: Health-related quality of life will be assessed with the St. George's Respiratory Questionnaire (SGRQ) and the Short-Form 36-Item Questionnaire (SF-36) prior to hospital discharge and following eight weeks of either the pulmonary telerehabilitation intervention or usual care. The SGRQ is a disease-specific questionnaire validated to measure health status in patients with COPD. Total SGRQ scores range from 0-100 with higher scores indicating greater symptoms burden. The minimal clinically important difference is a difference of four points in the total SGRQ score. The SF-36 consists of 36 questions spanning nine health domains and is a valid measure of health-related quality of life in COPD that is responsive to change following a pulmonary rehabilitation intervention.

Participant satisfaction survey: Participants will be administered a survey by the study coordinator after completion of the eight-week pulmonary telerehabilitation intervention that will require them to respond to statements related to their satisfaction with the home-based program using a five point Likert scale (strongly agree, agree, neutral, disagree, strongly disagree). Statements will address ease of use of the video conferencing modality, acceptability of exercise components, perceptions of impact on muscle strength and exercise endurance, and willingness to participate in additional pulmonary telerehabilitation. Questions regarding social support, psychiatric attributes, and other factors potentially associated with program adherence will also be asked in order to gain preliminary insights to optimize recruitment for a larger, randomized controlled trial of pulmonary telerehabilitation.

Please upload a table of procedures if applicable.

The study procedures table must be completed for:

- All Greater than Minimal Risk (GTM) studies; and
- All Minimal Risk studies that use Standard of Care or Usual Care/Interventions.

Name	Modified Date
Table of procedures	3/2/2021 12:56 PM

2.0

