The distributional characteristics of the outcome measures and change in outcome measures between study groups will be determined using appropriate descriptive statistics (e.g. mean, median, standard deviation, range) and graphical summarizations (e.g. histograms, boxplots, line plots). The purpose of this pilot study is to generate preliminary data on the expected effect size and variance of the outcome measures to facilitate planning (i.e. sample size calculations and power analyses) of a larger, randomized controlled trial. As such, we acknowledge that, given our small sample size (n=30, 15 participants per group), we likely will not have the power to detect a significant statistical or clinical difference in outcome measures between the intervention and usual care groups. However, we will perform exploratory analyses to compare changes in outcome measures between groups using a Student's t-test or nonparametric tests when appropriate.

ID: Pro00002952

View: 5 Sub-Studies

1.0 * Is there a sub-study or are there sub-studies associated with this study?

There is no sub-study associated with this study.

ID: Pro00002952

View: 6 Study Population Summary

Study Population Summary

1.0 * What is the maximum number of subjects you plan to enroll at VAPHS?

We plan to enroll 38 participants, accounting for 25% attrition, to result in 30 participants (15 intervention, 15 control) completing baseline and eight-week follow up testing.

2.0

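### The satisfaction survey has no stated time point for participants who stop telerehabilitation early, so acceptability and the adherence-factor questions would come mainly from completers

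*Combined protocol and SAP*

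**What the plan says.** SA 1, in the study objectives (View 2, 3.0), hypothesises high acceptance and adherence. It schedules the survey in one sentence: "A satisfaction survey will be administered at the completion of the intervention".

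The participant satisfaction survey paragraph (View 4, 1.0) says the same and names who gives it: "Participants will be administered a survey by the study coordinator after completion of the eight-week pulmonary telerehabilitation intervention". On content, it says: "Statements will address ease of use of the video conferencing modality, acceptability of exercise components", together with perceived benefit and willingness to do more, on a five-point Likert scale. The same paragraph adds: "Questions regarding social support, psychiatric attributes, and other factors potentially associated with program adherence will also be asked".

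On staffing, the intervention-group paragraph of View 4 has the home sessions run "via 1:1 video conferencing with the exercise physiologist/study coordinator". For the bedside sessions, the exercise-prescription paragraph says "the exercise physiologist/study coordinator will select the resistance setting on the cycle ergometer".

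On numbers, View 6, 1.0 states: "We plan to enroll 38 participants, accounting for 25% attrition", leaving 15 per arm who complete baseline and eight-week testing.

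The analysis plan (View 4.1) does not mention the survey, its denominator or missing responses. The visible text contains no exit survey and no early-termination contact.

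**The concern.** Both sentences that schedule the survey tie it to completing the programme. Someone who gave up because the video link, the cycle or the timetable did not suit them has no stated occasion to say so. Those answers are the most useful ones for redesigning the programme before a larger trial.

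Two results under SA 1 are exposed. The first is the acceptability figure, which would describe people who stayed. The second is the assessment of factors associated with adherence. Its questions sit in the same survey, so the least adherent participants would be missing from an analysis meant to explain low adherence. This second problem does not depend on the direction of any bias in satisfaction.

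A lesser point is who collects the ratings. The coordinator role gives the survey and may also run sessions, of which there are up to 24 per participant (8 weeks × 3). Nothing in the text prevents a participant from being asked to rate the programme by the person who delivered it.

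**Working it through.** **Timing, compared with the neighbouring outcomes.** In View 4, 1.0, the repeat six-minute walk, sit-to-stand test and quality-of-life questionnaires are timed by elapsed duration: once eight weeks have passed in either arm. The survey is timed by completion of the intervention. The difference in wording may be accidental, but as it stands the survey alone lacks a clock that runs for people who have stopped.

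**The plan's enrolment figure.** Inputs: 30 completers and 25% attrition (View 6, 1.0).
- 30 × 1.25 = 37.5, rounded up to 38. This reproduces the stated figure.
- Dividing by the retained share instead gives 30 / 0.75 = 40, or 20 per arm.

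**Participants left out.** Inputs: 1:1 allocation (View 2, abstract) and 15 intervention completers (View 6, 1.0). The documents also speak of randomising 30, so treating all 38 as randomised is an assumption.
- 38 / 2 = 19 in the intervention arm.
- 19 − 15 = 4 without a survey; 4 / 19 = 21%.
- With 20 in the arm: 20 − 15 = 5; 5 / 20 = 25%.

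**Size of the overstatement.** Let n be the arm size, c the completers, s the satisfied share among completers and a the satisfied share among stoppers. The share in the whole arm is (c·s + (n − c)·a) / n, and the completers-only survey reports s. The documents give neither s nor a, so both are assumptions.

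| n | c | s | a | Whole arm | Reported minus whole arm |
|---|---|---|---|---|---|
| 19 | 15 | 100% | 0% | 15/19 = 78.9% | 21.1 points |
| 19 | 15 | 100% | 50% | 17/19 = 89.5% | 10.5 points |
| 19 | 15 | 100% | 100% | 100% | 0 points |
| 19 | 15 | 90% | 20% | (13.5 + 0.8)/19 = 75.3% | 14.7 points |
| 19 | 15 | 90% | 50% | (13.5 + 2.0)/19 = 81.6% | 8.4 points |
| 20 | 15 | 100% | 0% | 15/20 = 75.0% | 25.0 points |

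**Precision.** With exact Clopper-Pearson 95% intervals, 15 of 15 satisfied is 100% (78 to 100%), and 15 of 19 is 79% (54 to 94%). The intervals overlap widely, as expected at this size. But sampling intervals do not cover the omission of stoppers, so a completers-only report would not reveal it.

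**The case against.** The strongest reply is that completion of the eight-week intervention may simply mean the week-8 time point for everyone in the arm. View 1 describes the programme as intention to treat, and someone who stops sessions but attends week-8 testing could be surveyed there. The uploaded survey form, follow-up checklist and procedures table might settle this, and they are not visible. This stands in part. A reader might infer that early stoppers are never asked, and the documents do not establish that. They show only that no time point for stoppers is stated.

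Second, attrition is not dissatisfaction. The 25% is loss from follow-up testing across both arms. The plan foresees other exits: withdrawal to join facility-based rehabilitation, and disqualification on safety grounds at the bedside sessions, before any home session. This stands. A reader might infer that the survey is biased upward as a matter of fact. That is the expected direction, but the bound starts at zero. A reader might also take 25% of 19 as 5 stoppers, leaving 14 completers, which gives gaps of about 10 to 18 points under the same assumed rates. The plan states 15 intervention completers, so 8 to 15 is the range that fits its figures.

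Third, on who collects the ratings, a reader might picture a face-to-face interview with the participant's own trainer. The mode is not stated, View 10.0 lists paper questionnaires, and other sections name only an exercise physiologist as running sessions and refer to coordinators in the plural. The text shows that one person could do both jobs, not that one person does.

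Fourth, adherence is tracked separately, so early stopping will be visible there. True, but adherence records that people stopped, not what they thought of the programme. It is also fair that no acceptability threshold is set, so no stated decision turns on a few responses.

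**Conclusion.** The point holds as a gap in the stated rule. As written, the acceptability result and the adherence-factor questions would come mainly from completers, leaving out about 4 of 19 in the intervention arm (5 of 20 under the other inflation formula).

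Satisfaction is likely, but not certainly, overstated: by 0 to 21 points if all 15 completers are satisfied, or about 8 to 15 points at 90% among completers and 20 to 50% among stoppers. These figures assume that all 38 are randomised equally, that loss from follow-up testing approximates stopping sessions, and that no stopper is surveyed. Any effect of who gives the survey cannot be sized from the documents.

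This is a cheap improvement to a descriptive pilot result. It does not threaten the trial's validity.

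**What to change.** Amend the SA 1 text in View 2, 3.0 and the survey paragraph in View 4, 1.0 as follows:

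- Offer the survey to every participant randomised to telerehabilitation, at week 8 or soon after stopping sessions, whichever comes first, by mail or telephone if needed.
- Add one item on the reason for stopping.
- Have it self-completed on paper or, where existing staff allow, given by a team member who did not run that participant's sessions.
- State in View 4.1 that responses are reported against the number randomised to the arm, with completers, early stoppers and non-responders shown separately.

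The cost is a short amendment and a small revision of the uploaded survey form. The weekly pedometer calls and paper questionnaires already provide the routes. The downsides are that some early stoppers will not reply and the satisfaction figure may look less favourable.

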*** Abstract. Please provide a brief description of the study.**

Pulmonary telerehabilitation programs have been shown to have a high acceptance and adherence rate and lead to improvement in exercise capacity and quality of life in stable COPD. However, data regarding the feasibility and impact of pulmonary telerehabilitation following hospitalization for an AECOPD on physical activity levels, muscle function, exercise capacity, and health-related quality of life are lacking. Our primary hypothesis is that a home-based pulmonary telerehabilitation program initiated at hospital discharge following an AECOPD is feasible in the veteran population and will result in increased physical activity and greater improvement in muscle function, exercise capacity, and health-related quality of life compared to usual care. We will test this hypothesis with the following specific aims: (1) To determine the feasibility of an eight-week home-based pulmonary telerehabilitation program in veterans with moderate to severe COPD initiated in the immediate post-hospitalization period following an AECOPD. (2) To determine physical activity levels and the magnitude and variability in changes of measurements of muscle strength, functional exercise performance, and health-related quality of life following an eight-week home-based pulmonary telerehabilitation program versus usual care initiated in veterans with moderate to severe COPD immediately following hospitalization for an AECOPD. We will randomize (1:1 allocation) 30 male and female veterans hospitalized with an AECOPD to either an eight-week, three sessions per week, home-based pulmonary telerehabilitation program that includes lower extremity endurance exercises with a cycle ergometer and upper and lower extremity strength training with 1:1 supervision via video conferencing with an exercise physiologist as well as an optional once -monthly support group via teleconferencing versus usual care. Changes from baseline in physical activity levels, handgrip and quadriceps muscle strength, exercise endurance, and health-related quality of life will be assessed following the pulmonary telerehabilitation program versus usual care. Findings from this project will contribute to the growing field of pulmonary telerehabilitation and will provide critical preliminary data for the design and implementation of a larger, randomized control trial assessing the impact of pulmonary telerehabilitation on long-term clinical outcomes following AECOPD.

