*** Do you plan on enrolling patients into different categories:**

Yes No

If yes, please explain:

We will randomize 30 eligible participants hospitalized with an acute exacerbation of COPD in a 1:1 allocation to either the eight-week home-based pulmonary telerehabilitation program intervention versus usual care prior to hospital discharge.

3.0 If this is a multi-site study, indicate the projected total subject accrual:

N/A

4.0*** Please provide a justification for the sample size:**

To meet our recruitment goal of 30 subjects over a one-year time interval, we will be required to enroll an average of 2-3 participants per month. A review of our COPD admission data shows that the medicine service at the VAPHS admits a mean of 28.4 (SD 8.7, range 15-43) patients per month with a primary diagnosis of COPD with acute exacerbation. Therefore, we anticipate no difficulty with recruitment for this study. We have not performed a sample size calculation given that this is a pilot study to generate preliminary data for the planning of a larger randomized controlled trial (including data to calculate estimated sample size).

ID: Pro00002952

View: 6.1 Study Population

Study Population**1.0 * Check all that apply to describe your study population:**

Study Population

 Non-Veterans Special Populations **Veterans** Vulnerable populations Other**2.0 * Indicate the inclusion criteria for enrollment:**

(1) Male and female veterans age 40-80; (2) Moderate or severe COPD with a forced expiratory volume in 1 second - forced vital capacity ratio (FEV1/FVC) < 0.70 and FEV1 < 80% predicted; (3) Hospitalization with a primary diagnosis of AECOPD, defined as an increase in shortness of breath, cough, and/or sputum production beyond the normal day-to-day variation necessitating a change in regular medication when other causes of increased shortness of breath, cough, and/or sputum production have been ruled out; (4) Capable of operating a tablet independently with adequate vision and hearing. The inclusion criteria should select for COPD patients with significant pulmonary disease that fall within an age range where age-related changes in muscle function are not the dominating factor.

3.0 * Indicate exclusion criteria for enrollment:

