[DSMB_charter.docx\(0.01\)](#)

ID: Pro00002952

View: 12 Costs and Payments

Costs and Payments

1.0 * Does this study have a budget?:
 Yes No
If yes, please upload the current budget:
[SPiRE budget.pdf\(0.01\)](#)

2.0 * Will patients receive payments for this study?
 Yes No
If yes, please upload the financial letter of support (either from the Business Service line or the Veterans Health Foundation) or documentation waiving the requirement of a letter of support:
[VA Financial LOS Memo v3 Sept2018.pdf](#) 0.02

3.0 * Are you paying patients using the WePay system?
not applicable

ID: Pro00002952

View: 12.1 Costs

Costs

1.0 * Will subjects be required to pay for any services outside of the VHA that may be required as part of participating in this research study?
No

ID: Pro00002952

View: 12.2 Participant Payments

Participant Payments

1.0 * Please explain how the proposed payments are reasonable and commensurate with the expected contributions of the subject:
The participants will be paid \$150 for participation in the study. They will be asked to perform baseline and 8-week six minute walk testing, muscle strength testing, sit-to-stand testing, and answer questionnaires. They will also be asked to wear a pedometer to monitor their physical activity for eight weeks. Participants

in the intervention arm will participate in a total of 24 pulmonary rehabilitation sessions. This payment is reasonable and commensurate with the number of procedures required and travel time.

2.0 * Please provide information on how the subject payments are fair and appropriate, and that they do not constitute (or appear to constitute) undue pressure or influence on the prospective research subjects to volunteer for, or to continue to participate in, the research study. In addition the payments do not constitute (or appear to constitute) coercion to participate in, or continue to participate in, the research study:

The payments will compensate for the subject's time and travel back to the facility for follow up testing. They do not constitute undue pressure or influence on the prospective research subjects to volunteer for, or to continue to participate in, the research study. Subjects are free to quit the study at any time and will still be able to keep their cycle ergometer and exercise bands if randomized to the intervention arm.

3.0 * Specify the amount, form of payment and the specific disbursement schedule of payments:

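### SA 1 looks for psychiatric and social-support correlates of adherence, but the only collection described follows the eight-week programme, so changeable factors are measured after adherence has accrued

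*Combined protocol and SAP*

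**What the plan says.** The aim is in the combined protocol and SAP, Study Summary 3.0, under SA 1: "We will also assess factors (i.e. psychiatric attributes, social support) associated with adherence to obtain preliminary insights". The stated use is recruitment to a larger trial. No time point is given for these factors. The same paragraph places the survey at the end: "A satisfaction survey will be administered at the completion of the intervention".

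The method is in Research Study Methods 1.0, Participant satisfaction survey. It opens "Participants will be administered a survey by the study coordinator after completion of the eight-week pulmonary telerehabilitation intervention" and later adds "Questions regarding social support, psychiatric attributes, and other factors potentially associated with program adherence will also be asked". No instrument or scale is named for either factor.

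In the paragraph just before it, the SGRQ and SF-36 are scheduled "prior to hospital discharge and following eight weeks of either the pulmonary telerehabilitation intervention or usual care", so a questionnaire sitting before the programme is already planned.

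Under Participant Payments 1.0, those "in the intervention arm will participate in a total of 24 pulmonary rehabilitation sessions", which is the eight weeks at three sessions per week over which adherence builds up. The analysis plan (View 4.1) covers between-group comparison of outcome changes and contains no analysis of adherence or its correlates.

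**The concern.** A factor is useful for planning recruitment if its value before the programme tells us who will attend. The plan as described records the value only afterwards. The programme offers one-to-one supervised contact three times a week and an optional support group, so it could plausibly change mood or the support a participant feels. Someone who attended well may report better support because of attending. Someone who struggled may report lower mood because of struggling.

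An association found this way could run in either direction, and later analysis cannot recover a baseline value that was never taken. What is at stake is the guidance that this part of SA 1 passes to the next trial. The comparison of the two arms under SA 2 does not depend on it.

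**Working it through.** The plan gives no figure on this point, so there is none to reproduce. The check has three parts.

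**1. Order of events, from the text.**
- Consent at the bedside (View 9.4).
- Randomisation before discharge (View 6, 2.0).
- SGRQ and SF-36 before discharge (Research Study Methods 1.0).
- At least one to two bedside rehabilitation sessions before discharge for the intervention arm (Study Interventions).
- Home sessions, starting one to six weeks after discharge: 8 weeks x 3 = 24.
- Survey with the psychiatric and social-support questions, after the programme.

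No psychiatric or social-support measure is named at any earlier step. Chart review and participant interview (View 10.0) and the baseline SF-36 could yield related information, but the text does not assign them to this purpose.

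**2. What late measurement can do (illustration; s, g and r are assumed, not taken from the documents).** Let X0 be the pre-programme factor and A the sessions attended, both standardised, with correlation r. Let the later answer be X1 = s·X0 + g·A + e, scaled to variance 1. Here s is the share of the earlier value that is kept and g is the shift caused by attendance. Then corr(X1, A) = s·r + g.

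| s | r | g | Observed correlation |
|---|---|---|---|
| 0.8 | 0 | 0.2 | 0.8 x 0 + 0.2 = 0.20 |
| 0.8 | 0.40 | 0 | 0.8 x 0.40 = 0.32 |
| 0.8 | 0.40 | 0.2 | 0.32 + 0.2 = 0.52 |
| 0.8 | 0.40 | -0.2 | 0.32 - 0.2 = 0.12 |
| 1 | 0.40 | 0 | 0.40 (fully stable factor) |

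Bedside answers carry error too. If they correlate 0.8 with the patient's usual state, and the error is unrelated to attendance, a true 0.40 shows as 0.8 x 0.40 = 0.32. That equals the late-measurement result with g = 0. The advantage of asking early therefore rests on g differing from zero, that is, on attendance affecting the answer.

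**3. Precision.** The analysis plan gives 15 participants per group. The Fisher interval for r = 0.40 is tanh(atanh(0.40) ± 1.96/√(15 - 3)) = tanh(0.424 ± 0.566), which gives -0.14 to 0.76. The largest shift from 0.40 in the table is 0.40 - 0.12 = 0.28. The interval extends 0.54 below and 0.36 above 0.40, so sampling error exceeds the illustrated bias.

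**The case against.** The strongest reply is that this is one exploratory sentence in a pilot, that nothing primary or comparative depends on it, and that chance error with 15 patients is larger than any plausible timing bias. That stands, and it keeps the point minor. It does not remove it: imprecision will be visible in the interval and is expected in a pilot, whereas an association read in the wrong direction would not show.

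A second reply is that the gap may not exist. The table of procedures, Baseline Visit Checklist, Participant Information Form and survey form are uploads whose content is not shown. Participant Payments 3.0 mentions pre-discharge questionnaires without listing them. The survey may also ask mainly about history or living situation, which late timing hardly affects. This stands as well: a reader might infer that no baseline information will be collected, but the documents support only that none is described.

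A third reply is that asking before discharge does not by itself keep the answers free of the programme. This is right. The trial is unblinded and intervention participants have bedside sessions before discharge, so the questions must come before both allocation and those sessions.

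A reader might also infer that people who stop early are not surveyed, and so that the poorest attenders are missing. The text ties the survey to the end of the programme but does not say who is approached. That is unclear rather than shown.

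**Conclusion.** The point holds in a limited form. For changeable factors, the collection described cannot separate what predicts attendance from what follows from it, while the stated use needs the former. Stable or historical factors are little affected.

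The conclusion rests on two things: that no unseen form already asks these questions at baseline, and that attendance has some effect on the answers. The documents give no figure for that effect. Whichever timing is used, the result stays exploratory and imprecise (-0.14 to 0.76 around 0.40 with 15 patients). It would be too strong to say that this part of SA 1 is invalid or that the treatment comparison is biased. This is a minor improvement that costs little now and cannot be made after the data are in.

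**What to change.** If one of the uploaded forms already asks these questions at baseline, say so in the Participant satisfaction survey paragraph, and the point is closed. If not, amend that paragraph and the baseline schedule as follows:

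- Ask the social-support and psychiatric questions with the baseline SGRQ and SF-36, after consent and before randomisation and the bedside rehabilitation sessions.
- Keep the satisfaction items at week 8.
- State in the analysis plan that the baseline answers will be related to sessions attended out of 24 for everyone randomised to telerehabilitation, including those who stop, and reported as an estimate with its interval.

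A planned weekly telephone call is a weaker substitute. It is usable only if it comes before the first home session, which may be as early as one week after discharge, and it would still follow allocation and the bedside sessions.

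The cost is a few more questions for a patient who is unwell, with the tiredness and possible embarrassment already listed as questionnaire risks, perhaps in a semi-private room. Some answers will reflect the acute illness. An IRB amendment is needed, but no new visit.
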